10.6.5. Safety Assessment

10.6.5.1. Extent of Exposure

Exposure to study drug for the Safety Population of the maintenance phase will be summarized for treatment duration, calculated as the number of days from the date of first randomized study medication taken to the date of last dose taken, inclusive. Descriptive statistics (n, mean, standard deviation, median, minimum, and maximum) will be presented by treatment group.

10.6.5.2. Adverse Events

An AE that occurs during the treatment period will be considered a TEAE if it was not present prior to the first dose of study drug or was present prior to the first dose of study drug but increased in severity during the treatment period. If the same AE is reported more than once prior to the first dose of study drug, the AE with the greatest severity will be used as the benchmark for comparison with the AEs occurring after the first dose of study drug that were coded to the preferred term.

All AEs will be classified by System Organ Class (SOC) and Preferred Term (PT) according to Medical Dictionary for Regulatory Activities (MedDRA). If more than one AE is coded to the same preferred term for the same patient, the patient will be counted only once for that preferred term using the most severe and most related occurrence for the summarization by severity and by relationship to the study drug.

The number, percentage and the corresponding 95% CI of patients experiencing TEAEs in each treatment group will be presented. The significance test for treatment difference will be carried out using χ^2 -test or Fisher's exact test.

Listings will be presented for patients with SAEs, patients with AEs leading to permanent discontinuation, and patients with AEs leading to death.

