8. STUDY OBJECTIVES

1. The primary objective is to demonstrate the therapeutic equivalence of PDA10 to Eprex[®] in patients with end stage renal failure (ESRD) on chronic hemodialysis.

The therapeutic equivalence shall be evaluated by the difference between treatment groups in the change in hemoglobin from baseline, while taking into account differences in epoetin dosage.

2. The secondary objective is to assess the safety and tolerability of PDA10
3. The aim of the open-label extension phase is to assess the long-term safety and tolerability of PDA10

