10.4.8. Expected Adverse Events and Precautions for Use

In larger overseas clinical studies of erythropoietin products conducted among patients with renal failure, a number of treatment-related side effects have occurred. Hypertension (24.7%) was the most commonly reported side effect, followed by muscle cramp, upper respiratory infection and headache, respectively reported in about 20% of subjects. Other frequently reported events were different types of infections, thrombosis (associated with hemodialysis in patients with renal failure), diarrhea, hypertension, dizziness, weakness, etc. whose incidence ranged 6~16%. Epileptic seizure was rarely reported at an incidence of 0.6%. In addition, a potential risk of infection with fatal pathogens such as

virus is suggested with the use of currently marketed erythropoietin products, which may be contaminated with animal-derived proteins during their cell culture process. Thus, the adverse events described above may occur during this clinical study. Based on the labeling information of Espogen Prefilled Syringe, a list of expected adverse events and precautions for use in this clinical study is prepared as follows:

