10.6. STATISTICAL METHODS

10.6.1. General Principles of the Result Analysis

Statistical analyses will be performed using the data analysis software SAS® Version 9.2 or higher.

Statistical testing will be done at alpha=0.05 level, two-sided, without any adjustment for multiple comparisons unless otherwise specified. The p-values will be rounded to 4 decimal places; p-values less than 0.0001 will be presented as “<.0001” in all tables.

Summaries of categorical variables (nominal or ordinal) will include frequency and percentage of patients at each level of response. Continuous variable summaries will include n, mean, median, standard deviation, minimum and maximum values.

The primary efficacy analysis will be based on the PP population.

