$k = n_c / n_t = 1$ (allocation ratio),

and $n_c = kn_t$ (the number of patients in the control group)

Consequently, the planned sample size to show the therapeutic equivalence between PDA10 and Eprex group is 126 patients per group. Considering that the chance to be excluded from the PP population is 20%, the total number of patients to be enrolled will be 316 (158 per group).

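### The only between-arm adverse-event analysis stated is a test of no difference; no stated output bounds how much worse PDA10 could be than Eprex

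*Protocol*

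**What the plan says.** Section 8 of the protocol makes safety the secondary objective: "The secondary objective is to assess the safety and tolerability of PDA10".

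Section 10.6.5.2 fixes three outputs for adverse events:

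- Within-arm summaries: "The number, percentage and the corresponding 95% CI of patients experiencing TEAEs in each treatment group will be presented".
- One between-arm inference: "The significance test for treatment difference will be carried out using χ^2 -test or Fisher's exact test". The synopsis (Statistical methods, Safety Analysis) repeats it.
- Listings for the most important events: "Listings will be presented for patients with SAEs, patients with AEs leading to permanent discontinuation, and patients with AEs leading to death".

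The general rule in 10.6.1 sets the level: "Statistical testing will be done at alpha=0.05 level, two-sided, without any adjustment for multiple comparisons unless otherwise specified".

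The trial size comes from the efficacy calculation in 10.6.7, which ends with "the total number of patients to be enrolled will be 316 (158 per group"). No power or precision is stated for any safety comparison. The protocol does give background adverse-event rates in 10.4.8, for example "Hypertension (24.7%) was the most commonly reported side effect", about 20% for muscle cramp, upper respiratory infection and headache, and 6 to 16% for other frequent events.

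**The concern.** For efficacy, the protocol uses the logic an equivalence trial needs: confidence limits for the difference, compared with margins (10.6.4.1). For adverse events it changes to a test of the hypothesis of no difference. In a biosimilar trial a non-significant result is what one expects if the products are alike. It is also what one may well see if they differ moderately and the trial was not sized to show it. The p-value alone does not separate these cases.

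An interval for the difference would separate them, because it shows which excesses the data exclude. None is stated. A reader of the planned tables would have two separate within-arm intervals and a p-value for TEAEs. For serious events, discontinuations and deaths there would be only a list of patients. At stake is how well the secondary objective can be answered. The primary endpoints are not affected.

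**Working it through.** **Inputs from the protocol.** Two-sided alpha 0.05 (10.6.1); 158 per arm (10.6.7.2); 1:1 allocation; a safety population of all who started randomized medication (10.6.2.1), so at most about 158 per arm; background rates of 24.7%, about 20% and 6 to 16% (10.4.8).

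**Input not in the protocol.** The size of a clinically relevant excess. The values below are assumptions, so a range is shown.

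**1. The planned size reproduces, and it is an efficacy size.** Hemoglobin: 2 × (1.645 + 1.96)² × 1.1² / 0.5² = 125.80, so 126 per arm. With 20% excluded: 126 / 0.80 = 157.5, so 158 per arm and 316 in total. No adverse-event rate enters.

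**2. Miss rate of the stated test.** With control rate p₁, test rate p₂, mean p̄ and n = 158:

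- SE under no difference: s₀ = √[2 p̄(1 − p̄)/n]
- SE under the assumed difference: s₁ = √[(p₁(1 − p₁) + p₂(1 − p₂))/n]
- Power ≈ Φ[(p₂ − p₁ − 1.96 s₀)/s₁]; miss rate = 1 − power

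For 24.7% versus 34.7%: p̄ = 0.297, s₀ = 0.0514, s₁ = 0.0511. Then (0.100 − 1.96 × 0.0514)/0.0511 ≈ −0.015, so power is 49.4% and the miss rate 50.6%. Exact enumeration of both tests gives:

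| Eprex vs PDA10 (assumed) | Miss, chi-square | Miss, Fisher |
|---|---|---|
| 24.7% vs 34.7% | 50.5% | 55.1% |
| 20% vs 30% | 46.0% | 50.9% |
| 6% vs 12% | 53.3% | 60.6% |
| 24.7% vs 39.7% | 18.2% | 21.5% |
| 10% vs 15% | 73.1% | 78.4% |

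The first three rows give "about half". The last two show how far that depends on the assumed excess. For 80% power the trial would need 327, 294 and 356 per arm for the first three rows.

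**3. What the p-value and the interval each show.** Take hypertension in 53/158 on PDA10 (33.5%) and 39/158 on Eprex (24.7%), a hypothetical result.

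- Chi-square p = 0.083; Fisher p = 0.107. Neither is significant.
- Within-arm 95% intervals (Wilson): 26.7 to 41.2% and 18.6 to 32.0%. They overlap.
- Difference: 8.9 points. Newcombe limits combine the Wilson limits. Lower: 0.0886 − √[(0.3354 − 0.2665)² + (0.3195 − 0.2468)²] = −0.012. Upper: 0.0886 + √[(0.4122 − 0.3354)² + (0.2468 − 0.1861)²] = +0.186.

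The same counts that give a non-significant test leave an excess of up to 18.6 points open. None of the stated outputs displays that figure.

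**4. Precision of the interval if added.** Half-width at equal rates is 1.96 √[2p(1 − p)/158]. At 24.7% this is 9.5 points; at 20%, 8.8; at 16%, 8.1; at 6%, 5.2.

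**The case against.** **A risk-difference column is ordinary SAP content, and the SAP is not shown.** This is fair as to table layout, and the SAP may already contain it. But the protocol did not leave the comparison open. It names a method for the treatment difference, in the body and in the synopsis, and that method suits the question poorly.

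**The per-arm counts and intervals already hold the information.** For TEAEs they do, and a reader could derive the difference interval from them. But the two intervals do not bound the difference as displayed, and for serious events, discontinuations and deaths the protocol states no by-arm summary at all.

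**A reader might infer that the protocol will treat p > 0.05 as proof of comparable safety.** The text does not support this. It states no such rule, sets no safety margin, and gives safety an objective of assessment only. Equivalence is claimed for hemoglobin and dose alone.

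**A reader might infer that the test usually fails to find a relevant harm.** This is not supported either. Relevance is undefined in the document, and some of the assumed excesses are detected more often than missed: 20% versus 30% in 54% of trials by chi-square, 24.7% versus 39.7% in 82%.

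**The rates and the unit of testing are uncertain.** The background rates come from larger overseas studies. This trial enrols patients already on erythropoietin and excludes uncontrolled hypertension, so its own rates may differ. Nor is it clear that the test is run for each event as well as for any TEAE, for which no rate is given. Both points stand, so the miss rates are illustrations.

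**The interval does not make the trial larger.** True. Precision is set by the sample size. The gain is that the limits of the evidence become visible.

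**Conclusion.** The point holds as a weakness in a stated analysis choice; no figure in the protocol is wrong. As written, the only between-arm adverse-event inference is a test of no difference, and no stated output bounds the excess on PDA10. That conclusion rests on the text of 10.6.5.2 and the synopsis and needs no assumption about rates.

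Its size does need assumptions. For a 10-point excess on rates of 20 to 24.7%, or a doubling of a 6% event, the chi-square test misses 46 to 53% of the time at 158 per arm, and Fisher's test somewhat more. Across the other excesses shown, the chi-square miss rate runs from 18% to 73%. A non-significant result could therefore be over-read; the protocol does not say that it will be. The change is a cheap improvement that should be made, and it does not touch the primary analysis.

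**What to change.** In 10.6.5.2 and the matching synopsis text, state that for the maintenance phase the difference in proportions (PDA10 minus Eprex) will be presented with its two-sided 95% confidence interval, by the Newcombe or the Miettinen-Nurminen method. The interval may replace the test or stand beside it.

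Apply it to any TEAE, SAEs, AEs leading to discontinuation, hypertension, and thrombotic or vascular-access events, and keep the listings. Say that the between-arm safety statement will be based on this interval. The maintenance phase is the right window because every patient in the extension receives PDA10.

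The cost is a wording change and one extra column in the adverse-event tables, with no new patients or data. The intervals will be openly wide, about ±9.5 points at a 24.7% rate.

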10.6.5.3. Vital Signs

Descriptive statistics for vital signs and changes from baseline at each visit will be presented by treatment group.

A supportive listing of patients with clinically significant abnormal postbaseline values will be provided, including the Patient ID, study center, and baseline and postbaseline values.

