10.3.2. Exclusion Criteria

Patients who meet any of the following criteria will not be eligible to participate in the study:

1. Patients with a temporary or permanent catheters or synthetic grafts
2. Patients with uncontrolled hypertension, defined as a pre-dialysis diastolic BP of greater than 110 within 12 weeks prior to randomization
3. Patients with severe disease within the last 6 months prior to randomization (e.g stroke, transient ischemic attack, myocardial infarction, cerebrovascular accident, coronary artery bypass graft deep venous thrombosis, unstable angina, decompensate congestive heart failure (New York Heart Association [NYHA] class III~IV), or other thromboembolic event
4. Surgery patients who for any reason cannot receive adequate antithrombotic prophylaxis or treatment
5. Patients with a current or recent known history of a severe hyperparathyroidism or PTH > 1500 pg/ml within 12 weeks prior to randomization-

6. Patients with hyperkalemia
7. Patients with epilepsy
8. Patients with malnutrition (serum albumin < 3.5g/dl prior to randomization)
9. Patients with an acute infection, acute hepatitis (including A, B, C type) or chronic hepatitis B or C requiring treatment or HIV infection
10. Patients with significant inflammation (CRP >30 mg/L within 12 weeks prior to randomization)
11. Patients with a history of gastrointestinal bleeding within the last 6 months before Screening
12. Patients with any active, uncontrolled systemic or inflammatory disease that in the Investigator's opinion may be significant to exclude participation in the study
13. Patients of need for blood transfusions within 12 weeks prior to randomization
14. Patients with history of pure red cell aplasia (PRCA) or anti-erythropoietin antibodies
15. Patients with a history of malignancy of any organ system within the last 5 years prior to Screening
16. Patients with a current diagnosis of anemia due to folic acid and/or Vitamin B12 deficiencies, hemolysis, or gastrointestinal bleeding or a history of/ or active blood or bleeding disorders within the last 6 months before Screening
17. Patients who have received immunosuppressive treatment or use of other medication known to influence erythropoiesis 12 weeks prior to randomization
18. Patients with hypersensitivity to the active substance or to any of the excipients
19. Patients who have treated with any other investigational drug within 4 weeks prior to Screening
20. Patients who currently are pregnant or lactating

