10.4.2. Identity of Investigational Product(s)

The Sponsor will provide the study drugs packaged in a double-blind configuration in labeled containers and each subject's study drug will consist of either PDA10 or Eprex[®] during the maintenance phase. Each study center will be provided with drug supplies corresponding to a sequence of randomization numbers.

The properties of the investigational product provided by the Sponsor are listed in the table below.

PDA10 for intravenous injection is supplied in a pre-filled syringe (PFS).

Investigational Products	Appearance
Investigational Product: PDA10	Formulated as a sterile, colorless liquid in an isotonic sodium chloride/ sodium phosphate buffered solution in pre-filled syringe
Reference Product: Eprex [®]	Formulated as a sterile, colorless liquid in an isotonic sodium chloride/ sodium phosphate buffered solution in pre-filled syringe

Storage conditions

PDA10 and Eprex[®] are to be stored between 2°C and 8°C in the refrigerator, away from the freezer compartment and kept in the original carton. This temperature range should be closely maintained until administration to the subject.

The product should not be used, and discarded

- if the seal is broken,
- if the liquid is colored or particles floating is observed,
- if it may have been accidentally frozen, or
- if there has been a refrigeration failure

Note:

The investigational products should be visually inspected for particulate matter and discoloration prior to administration. Product exhibiting particulate matter or discoloration must not be used. The PFSSs should not be shaken; shaking may denature the glycoprotein, rendering it inactive.

The investigational products contain no preservatives, and the syringe should not be reused and unused portion must be discarded.

IV Injection should be administered over 1-2 minutes. In subjects on dialysis the injection should follow the dialysis procedure. Slow injection over 5 minutes may be beneficial to those who experience flu-like symptoms.

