10.5.3.5. Vital Signs

Vital sign measurements will be documented at every visit before administration of study medication. The parameters will include sitting pulse rate and sitting systolic and diastolic blood pressure. Pulse rate and blood pressure readings will be taken after the subject has been sitting for 5 minutes; the same arm should be consistently used for the measurements. Subjects found to have abnormal blood pressure will be evaluated by the PI to ensure to determine if they are eligible to continue in the study.

- Pulse
- Systolic/diastolic blood pressure

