10.6.5.5. Clinical Laboratory Test

Descriptive statistics for clinical laboratory values and changes from the baseline values at each visit will be presented by treatment group for each clinical laboratory parameter. Also, the shift-table of change of status from the baseline to the last visit will be presented for each clinical laboratory parameter. Listings will be presented for patients with clinically significant abnormal values.

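### Blood pressure is not timed relative to dialysis, so change from baseline can mix unlike readings, and the laboratory shift table uses only the last visit, so it can omit transient abnormalities

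*Protocol*

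**What the plan says.** **Blood pressure.**
- Protocol 10.5.3.5: "Vital sign measurements will be documented at every visit before administration of study medication". It also fixes sitting posture, five minutes' rest and a consistent arm, but gives no point relative to the dialysis session.
- Protocol 10.4.1 describes the injection as not depending on dialysis. It allows the injection into the venous line when dialysis ends, or as a bolus while the session is running.
- Protocol 10.4.2: "In subjects on dialysis the injection should follow the dialysis procedure".
- Protocol 10.3.2, exclusion 2, does name a dialysis time point: "Patients with uncontrolled hypertension, defined as a pre-dialysis diastolic BP of greater than 110 within 12 weeks prior to randomization".
- Protocol 10.6.5.3: "Descriptive statistics for vital signs and changes from baseline at each visit will be presented by treatment group". It adds: "A supportive listing of patients with clinically significant abnormal postbaseline values will be provided". No numeric limit is attached.

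**Laboratory values.**
- Protocol 10.6.5.5 gives by-visit summaries and a patient listing of clinically significant values. It also fixes the form of the categorical table: "the shift-table of change of status from the baseline to the last visit will be presented for each clinical laboratory parameter".
- The schedule in 10.5.5.1 places full hematology and biochemistry panels every four weeks in the maintenance phase.

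**The concern.** Safety is the secondary objective. Section 10.4.8 says of earlier epoetin studies: "Hypertension (24.7%) was the most commonly reported side effect". Blood pressure is therefore the vital sign on which a reader will most want a clean comparison.

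The protocol treats dialysis timing as material when it defines uncontrolled hypertension for eligibility, then drops it when it defines the on-study measurement. If a baseline reading is taken before dialysis and a later one after it, the difference contains the effect of the session as well as any effect of the drug. How the data are collected cannot be repaired at the analysis stage. The same readings also serve the principal investigator's assessment, in 10.5.3.5, of whether a subject with abnormal pressure may continue.

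For laboratory values, section 10.4.8.1 expects occasional rises in liver enzymes and serum potassium. Such rises can come and go. A table that looks only at the final visit does not show one that has resolved, and similar last-visit tables in the two arms could be read as similar laboratory safety throughout.

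**Working it through.** The plan states no figure on this point, so there is none to reproduce.

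**Step 1. When can a compliant blood pressure reading be taken?** The only condition is that it precedes the injection.

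| If the injection is | Source | A pre-dose reading may be |
|---|---|---|
| unrelated to dialysis | 10.4.1 | at any point relative to a session |
| during the session | 10.4.1 | before or during dialysis |
| at the end of or after the session | 10.4.1, 10.4.2 | before, during or after dialysis |

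The last row shows that reconciling 10.4.1 with 10.4.2 is not enough. Even if every injection followed dialysis, the reading could fall anywhere up to that moment. The measurement needs its own anchor.

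**Step 2. What this does to change from baseline.** Write the observed change as

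Y = D + (o_F − o_B),

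where D is the change at a fixed dialysis point, and o_F and o_B are the offsets due to timing at follow-up and at baseline.

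- Between arms: if the mix of timings is the same in both arms, the mean of (o_F − o_B) is the same in both and cancels from the arm difference. Section 10.4.5 supports this, because the maintenance phase is blinded and randomization is stratified by country and site.
- Spread: if the offsets are unrelated to D, Var(Y) = Var(D) + Var(o_F − o_B). The spread grows unless each patient's timing is constant.
- Within an arm: if timing drifts systematically after baseline, the mean change shifts in both arms and no longer describes the drug.

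The protocol gives no blood pressure standard deviation and no pre- to post-dialysis difference, so none of these terms can be given a number.

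**Step 3. How much of the laboratory follow-up the shift table uses.** Full panels fall at Weeks 4, 8, 12, 16, 20, 24 and 28, which is seven visits. I take the last visit to be the last maintenance visit, because 10.6.9 places the first study report after that phase. For a completer the table then uses Week 28 only, one of seven.

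Assume an abnormality is present at k of the seven visits, with its position random. The chance that Week 28 is among them is k/7:

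| k | shown at last visit | not shown |
|---|---|---|
| 1 | 1/7 = 14% | 86% |
| 2 | 2/7 = 29% | 71% |
| 3 | 3/7 = 43% | 57% |

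Early, resolving abnormalities would be shown less often than this, and late or persistent ones more often. For a patient who withdraws, the last visit may be the one that captures the abnormality.

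**Step 4. Where else could a transient abnormality be counted by arm?** By-visit summaries do not count patients, and the listing gives no total per arm. The remaining route is the table of treatment-emergent adverse events in 10.6.5.2. It receives the finding only if the investigator judges it clinically relevant under 10.5.3.1.

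**The case against.** A reader might infer that hypertension is summarised only through mean blood pressure and that affected patients are never counted by arm. The protocol does not support either reading.
- Section 10.6.5.2 codes adverse events by preferred term and gives number, percentage, 95% CI and a test of treatment-emergent events by arm. It includes events present before dosing that became more severe.
- Section 10.5.3 sends clinically significant new findings, and aggravation of existing disease, to adverse event assessment. Investigator judgment does filter these findings, but it is blinded in maintenance.
- Section 10.6.1 goes beyond means: "Continuous variable summaries will include n, mean, median, standard deviation, minimum and maximum values".
- Hemoglobin outside the target range during maintenance is a secondary endpoint compared by arm.

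Nor can the case rest on the weakness of a mean. Suppose 5% more of one arm rose by 25 mmHg. The mean would move 0.05 × 25 = 1.25 mmHg. With 158 per arm and an assumed SD of change of 10 to 15 mmHg, the standard error, SD × √(2/158), is 1.13 to 1.69, the 95% half-width 2.2 to 3.3 mmHg, and power about 20% down to 11%. But the plan does not test mean blood pressure, and a count is not clearly better: 24.7% against 29.7% at 158 per arm has about 17% power.

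Counts of patients above a blood pressure threshold, or with new antihypertensive treatment, are tables that a statistical analysis plan commonly supplies. None was available here, so their absence is no fault. The diastolic limit of 110 is an eligibility criterion, and the documents do not present it as a safety threshold.

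Two further objections carry weight without disposing of the point. Posture, rest and arm are standardised, and the same rule applies to both arms, so differential bias is not shown. A baseline-to-last-visit shift is also a conventional table, and clinically relevant transient abnormalities can still be reported as adverse events. What remains is that the protocol itself sets a loose time point for blood pressure and the narrower version of the shift table.

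**Conclusion.** The point holds as a modest, inexpensive improvement to the safety data. It does not show that a known harm goes uncounted.

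- Blood pressure: the protocol permits readings before, during or after dialysis, and its sections on injection timing conflict. The consequence is extra noise in change from baseline in both arms. That there is no bias between arms rests on both arms having the same mix of timings. That individual patients' timing actually varies is possible under the text but not demonstrated.
- Laboratory shifts: for completers the table uses one of seven scheduled panels. The 14%, 29% and 43% capture figures rest on random placement of the abnormality. The one-in-seven count applies to the four-weekly panels. Hemoglobin and hematocrit are measured every two weeks, and CRP, PTH and iron less often.

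The primary equivalence analysis is untouched. What gains is the comparative safety description.

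**What to change.** 1. **Section 10.5.3.5:** name one blood pressure measurement point relative to the dialysis session, the same at baseline and at every later visit. Pre-dialysis would match the reading used in exclusion 2.
2. **Sections 10.4.1 and 10.4.2:** reconcile the statements on when the injection is given relative to dialysis. This review takes no position on which is right.
3. **Section 10.6.5.5:** keep the last-visit shift table and add one from baseline to the worst post-baseline value in the maintenance phase, by arm. Define worst for each parameter, with separate high and low tables where both directions matter, and say whether retests count.

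By-arm counts for blood pressure thresholds and antihypertensive use are optional and can be left to the statistical analysis plan.

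The cost is one sentence on measurement timing, one reconciliation and one additional table from data already collected. The downside is that worst-value shifts look higher than last-visit shifts in both arms, which is why the two tables should be shown together.
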